9.1 Study Design

This will be a multinational, long-term, prospective observational cohort study using primary and secondary data collected by established international HSCT registries: the EBMT Registry and the CIBMTR Registry. The justification for leveraging these existing registries as key sources of data for this study is provided in Annex 1. The assessment of the registries is provided in Annex 2 (EBMT) and Annex 3 (CIBMTR).

The study will follow patients who received exa-cel for treatment of TDT or SCD following approval of the therapy in Germany, France, Italy, and UK (via EBMT) and US (via CIBMTR). The representativeness of the EBMT and CIBMTR Registries for transplant-eligible TDT and SCD populations in their respective regions is discussed in Section 9.2. Data on a broad range of safety and effectiveness outcomes, as well as important covariates, will be collected within EBMT and CIBMTR Registries via existing and custom, study-specific reporting forms.

The study enrollment period will continue for approximately 3 years following approval of exa-cel, with potential for enrollment expansion to up to 5 years if the target sample size is not reached (see Section 9.5). Eligible patients with TDT or SCD who are treated with exa-cel at the participating transplant centers reporting data to EBMT or CIBMTR and who consent to study participation will be included in TDT and SCD Exa-cel Cohorts. If any patients from participating centers receive exa-cel infusion prior to the study protocol approval, such patients will be considered for study inclusion. Included patients will be followed for up to 15 years after the administration of exa-cel. In addition, comparator populations of patients with TDT or SCD receiving an allo-HSCT within the participating transplant centers will also be followed for up to 15 years after transplant.

Measures to ensure long-term follow-up will include a combination of both transplant center and patient-specific interventions. In addition to standard patient-tracking routines, transplant centers participating in this sponsored study may receive additional education, patient tracking support, and/or tracking incentives based on annual patient follow-up.

For each included exa-cel-treated and allo-HSCT-treated patient, data will be captured for the baseline pre-transplant period, immediate peri-transplant period (pre-transplant conditioning regimen, cell infusion / Day 0, first 100 days), 6 months after transplant and annually thereafter throughout the 15-year post-transplant period (see schedule of data collection in Section 9.3.6). Long-term safety and effectiveness outcomes among exa-cel recipients will be evaluated within the TDT and SCD Exa-cel Cohorts comparing the post-transplant period to the pre-transplant period, as appropriate. Comparison of the key outcomes to the allo-HSCT-treated comparator groups will also be performed. Findings will be discussed in the context of available literature on the natural history of TDT and SCD under the medical standard of care, as appropriate.

Analyses will be performed by each registry separately (EBMT: data from Germany, France, Italy, UK; CIBMTR: US). Furthermore, within each registry, analyses will be performed separately for the TDT and SCD populations. In addition to the separate analyses within each registry, pooled analyses of key safety outcomes (Section 9.3.3) are planned at pre-specified timepoints (after 5-, 10-, and 15-year duration of follow-up is accrued for all enrolled patients).

In addition, participating EBMT and CIBMTR transplant centers will be trained to collect and report directly to the Marketing Authorization Holder (MAH) information on all serious adverse events (SAEs), regardless of causality, among exa-cel recipients starting at the time of exa-cel infusion and throughout the course of the study. All SAEs reported by the centers for the exa-cel treated study participants (Section 11) will be summarized in the study progress reports, interim analysis reports, and final study report.

Should a hematologic malignancy be diagnosed among any patient receiving exa-cel, participating centers will be instructed to contact the MAH to report the event and determine appropriate samples for analysis (Section 12). The MAH will follow the testing strategies described in Section 12 to assess whether the malignancy developed as a result of off-target editing.

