9.1.2 Inclusion and Exclusion Criteria

This study will have broad inclusion and minimal exclusion criteria. To be eligible for inclusion, patients must be:

- receiving an HSCT from a study-participating transplant center reporting data to the respective transplant registry; and
- receiving exa-cel or allo-HSCT for treatment of TDT or SCD from the date of approval of exa-cel through the end of the enrollment period.

For the Allo-HSCT Cohorts, patients must be of an age that corresponds with the exa-cel label current at the time of transplant.

All patients must additionally provide informed consent / assent for registry / study data collection.

For the Allo-HSCT Cohorts, patients receiving transplants with any donor type and cell source used during routine standard of care will be eligible for study enrollment.

Patients treated with alternative gene therapies or experimental therapies will not be included. No additional exclusion criteria will be implemented.

The inclusion criteria may be further modified as appropriate, e.g., to allow transplant centers from European countries other than Germany, France, Italy, or UK to be included if exa-cel becomes available during the proposed study enrollment period in those countries.

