This study will include patients from Germany, France, Italy, UK, and US. Within Europe, Italy, France, and UK are among the top providers of HSCT to patients with TDT and SCD (EBMT data on file).⁶ The US is among the top international providers of HSCT to patients with SCD (CIBMTR data on file). Within these 5 countries, study enrollment of both exa-cel-treated and comparator populations will take place from the participating transplant centers providing exa-cel commercially. Therefore, it is anticipated that patients receiving exa-cel post-authorization will be reflective of the eligible population in the target commercial regions and that the allo-HSCT comparators will similarly reflect the Exa-cel Cohorts' target age group for the region(s) and will receive comparable care. As indicated in Sections 9.1.1 and 9.1.2, all patients receiving exa-cel from participating transplant centers will be invited to enroll in the study. Patients receiving an allo-HSCT of any donor type or cell source and who are of an age that corresponds with the approved exa-cel label will also be invited to enroll and participate in the comparator group of the study.

All patients choosing to participate in the study will be enrolled by the transplant center at or before the time of transplant. The transplant centers have standardized forms and timepoints for reporting patient data to the patient registries. Baseline data and transplant specifics are collected by transplant centers and entered into the registry at or near the time of transplant ("Day 0"). Follow-up reporting of each individual patient's status occurs by the transplant center to the registry at standardized time intervals: 100 days, 6 months, 1 year, and then annually post-transplant. Study-specific data collection will be integrated into the transplant center reporting timelines. Patient data may be sourced by transplant center personnel directly from the transplant site or via the patient's routine healthcare provider (HCP). Further information on the data to be collected and the schedule of data collection can be found in Section 9.3 (Variables).

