9.7 Data Analysis

All analyses for this study will be performed by the respective statistical / programming teams using SAS, SPSS, R, or equivalent statistical software. All outcome variables specified in Sections 9.3.3 through 9.3.5 will be evaluated for both the exa-cel and allogeneic HSCT cohorts, including the TDT Exa-cel, TDT Allo-HSCT, SCD Exa-cel and SCD Allo-HSCT Cohorts. Patient-level data (pseudonymized) will additionally be available, for both exa-cel and allo-HSCT cohort participants, with patient consent / assent.

To meet the study objectives, data will be analyzed separately for each registry and each cohort at pre-specified timepoints over the study duration. Each interim report will include separate analyses of the data collected by each registry and will provide a descriptive comparison of the EBMT and CIBMTR patient populations in terms of (i) demographic and clinical characteristics, (ii) treatment(s) received, and (iii) outcomes. In addition to the separate analyses within each registry, pooled analyses of key safety outcomes (Section 9.3.3) will be performed at prespecified timepoints (after a 5-, 10-, and 15-year duration of follow-up is accrued for all enrolled patients), unless substantial heterogeneity is observed between the two registries. Any potential issues precluding variable harmonization across the two registries will be discussed in the analysis reports. Pooled analysis of additional outcomes may be performed if feasible and warranted. The results of the interim and final analyses will be presented in interim and final study reports.

Descriptive statistics will be presented for all study outcomes:

- **Continuous variables** will be summarized using the following descriptive summary statistics, where appropriate: the number of observations, mean, standard deviation, 95% CI, median, minimum value, maximum value, and 25th and 75th percentile values.
- **Categorical variables** will be summarized using counts, percentages, and 95% CIs, as appropriate.

Crude risks, crude relative risks with 95% CI, and odds ratios with 95% CI will be calculated for outcomes, as appropriate. Cumulative incidence, treating death as a competing risk, will be calculated and presented for select safety outcomes. Overall survival curves will be produced.

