9.7.1 Definition of Study Periods

For safety and effectiveness outcome analyses within the Exa-cel and Allo-HSCT Cohorts the pre-transplant and post-transplant periods will be defined as described below and illustrated in Figure 2:

- **Day 0 (transplant date)** is defined as the day of exa-cel product or allogeneic donor cell infusion, depending on cohort, as reported to the registries.
- **The pre-transplant / baseline period** will be broadly defined as the period prior to Day 0, with the length of the period varying depending on the study measures being evaluated:
 - For the *primary disease severity* measures (see Section 9.3.4 Effectiveness Outcome Variables) and *disease-related therapies* (see Section 9.3.5), the baseline period will be defined as 1 year prior to initiation of the conditioning regimen.
 - For *laboratory measures*, baseline will be defined as the non-missing measure most proximal, but prior to treatment initiation. This includes effectiveness measures such as total Hb, Hb fractionation (e.g., % HbS for SCD) and serum ferritin (see Section 9.3.4) as well other laboratory measures (see Section 9.3.5).
 - For pre-transplant *disease-related end-organ damage or dysfunction* (see Section 9.3.5) baseline will be defined as any time prior to the transplant.
 - Other variables such as patient demographics, pre-transplant height, weight and health status will be as reported at the most recent time point prior to transplant.
- The post-transplant period will continue for up to 15 years after the final enrolled patient's Day 0. For each patient, Year 1 will include events, new diagnoses or findings, and/or therapies initiated (or continued) within the first 365 days after Day 0; Year 2 will include the same occurring from patient day 366 to day 730, etc. Year 1 will further include the following time intervals based on existing transplant registry reporting: Day 0 to Day 100, Day 100 to 6 months, and 6-month to 1-year reporting. All patients, both exa-cel treated or comparator, will be followed for up to 15 years. Patients will be censored to last reported timepoint only after 2 years of loss to follow-up.

Figure 2 Study Periods

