10 PROTECTION OF HUMAN SUBJECTS

10.1 Subject Information and Informed Consent

Informed consent and/or informed assent will be collected for all study participants. The patient or patient's guardian (if the patient is a minor) will be provided with appropriate forms at the transplant centers prior to any data collection. Patients who are minors at the time of assent may be requested to re-confirm their individual consent / assent when they reach the age of majority, as specified by country.

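### The enrolment rules conflict and exempt only already-infused exa-cel patients, so early exa-cel mortality can be understated against allo-HSCT

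*Protocol*

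**What the plan says.** Four parts of the protocol bear on when a patient may enter.

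- **Section 9.1 (Study Design)**, on exa-cel: "If any patients from participating centers receive exa-cel infusion prior to the study protocol approval, such patients will be considered for study inclusion". The sentence on the allo-HSCT comparator that follows has no such provision.
- **Section 9.2 (Setting)**, on everyone: "All patients choosing to participate in the study will be enrolled by the transplant center at or before the time of transplant".
- **Section 9.1.2 (Inclusion and Exclusion Criteria)** sets one window for both treatments by transplant date: "receiving exa-cel or allo-HSCT for treatment of TDT or SCD from the date of approval of exa-cel through the end of the enrollment period". It adds: "All patients must additionally provide informed consent / assent for registry / study data collection".
- **Section 10.1** places consent first: the patient or guardian "will be provided with appropriate forms at the transplant centers prior to any data collection".

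Time is counted from infusion whatever the enrolment date. Section 9.7.1 says Day 0 "is defined as the day of exa-cel product or allogeneic donor cell infusion, depending on cohort, as reported to the registries". Its only rule on person-time concerns the end of follow-up: "Patients will be censored to last reported timepoint only after 2 years of loss to follow-up". Section 9.7 plans crude risks and relative risks, and adds: "Cumulative incidence, treating death as a competing risk, will be calculated and presented for select safety outcomes. Overall survival curves will be produced".

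**The concern.** A patient who enters a cohort some months after infusion, and had to be alive to consent, cannot contribute a death in those months. If follow-up is still counted from Day 0, that stretch adds person-time but no deaths. Patients who died in the same stretch and were never approached are absent altogether. This is left truncation handled as if it were full follow-up, and it lowers the mortality estimate.

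The comparison is also affected. An allo-HSCT patient transplanted in the same months meets section 9.1.2 but is shut out by section 9.2, and section 9.1 offers no exemption. Only the exa-cel cohorts would then carry the survivor-selected group. Mortality is one of the safety outcomes in section 9.3.3, and both primary objectives in section 8.1 depend on it, the second as a comparison with allo-HSCT. The limitations in section 9.9 discuss differential loss to follow-up but not late entry.

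**Working it through.** The plan gives no figure to reproduce here, so the check has two parts: the entry rules side by side, and an illustration of size.

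**1. The rules for a patient transplanted after exa-cel approval but before protocol approval**

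| Section | Exa-cel | Allo-HSCT |
|---|---|---|
| 9.1.2, transplant-date window | eligible | eligible |
| 9.2, enrolment at or before transplant | excluded | excluded |
| 9.1, infused before protocol approval | may be considered | no provision |

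The three cannot all hold, and the only stated exemption is for exa-cel.

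**2. Could the group be more than a handful?** The title page dates version 2.1 to 15 November 2024 and treats approval of the final protocol as still to come. Section 9.1 gives about 3 years of enrolment from exa-cel approval, and Table 1 expects it to end on 31 December 2026, so the window opens around January 2024. At least 10.5 of 36 months then precede approval: 10.5/36 = 29% under uniform accrual. Slow early uptake would lower this share. The range used below is 10% to 30%.

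**3. Size.** Inputs, all assumed: late-entry share *f* and true 1-year mortality *m*, with *m* equal in both arms.

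*Upper bound: all first-year deaths precede late entry.* Observed exa-cel risk = (1 − f) × m, so the spurious relative risk is 1 − f. At m = 5% and f = 20%: 0.80 × 5% = 4.0% against 5.0%, a ratio of 0.80. At f = 10% and 30% the ratios are 0.90 and 0.70.

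*Constant hazard, late entry spread evenly over 3 to 12 months.* For m = 5%:

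- Hazard = −ln(0.95) = 0.0513 per year.
- Mean time from entry to year 1 = 1 − (0.25 + 1)/2 = 0.375 year.
- First-year risk seen in late entrants ≈ 1 − exp(−0.0513 × 0.375) = 1.9%.
- Cohort estimate ≈ (1 − f) × 5% + f × 1.9%, which is 4.7%, 4.4% and 4.1% at f = 10%, 20% and 30%.

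A simulation of the same setting compares Kaplan-Meier counted from Day 0 with Kaplan-Meier using delayed entry:

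| True 1-year mortality | f | From Day 0 | Delayed entry |
|---|---|---|---|
| 5% | 10% | 4.75% | 5.05% |
| 5% | 20% | 4.38% | 4.98% |
| 5% | 30% | 4.11% | 5.02% |
| 10% | 10% | 9.4% | 10.0% |
| 10% | 20% | 8.9% | 10.0% |
| 10% | 30% | 8.2% | 9.9% |

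The ratio of uncorrected to true mortality is about 0.95, 0.88 and 0.82 as f rises. Delayed entry recovers the truth within simulation error.

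*Front-loaded deaths.* Assume 70% of first-year deaths fall within 100 days, evenly spread within each interval, and consent is uniform over 0 to 10.5 months. With m = 5%, late entrants show about 1.7%. At a 29% share the cohort shows 0.71 × 5% + 0.29 × 1.7% = 4.0%, or 4.1% once the late share is reduced for those who die before consent. At a 10% share it shows 4.7%. With m = 10% and a 29% share it shows 8.2%.

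**The case against.** The case against runs as follows.

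- **Survival to consent is inferred.** Section 9.1.2 refers to registry or study consent. Both registries take their own consent independently of this study (sections 10.1.1 and 10.1.2). A patient who gave registry consent at transplant and then died might be includable. This stands: the protocol does not say either way, so the bias applies only to those without prior consent.
- **The one-sidedness depends on how sections are combined.** Section 9.1.2 alone would admit earlier allo-HSCT patients. This also stands, but it is why the sections need reconciling.
- **Non-fatal events are not lost.** A reader might infer that the whole interval from infusion to consent is event-free for every outcome, so that engraftment and malignancy results are also tilted towards exa-cel. The documents do not support that. Section 9.1 has first-100-day data captured for each included patient, and section 11.3 covers serious events at any time after infusion. Only death, or an event that prevents consent, is removed. Section 9.9.5 notes that patients who do best may reduce contact, so late consent could even over-represent patients with problems.
- **Selective entry.** A reader might take the promise only to consider such patients as licence to choose. The Abstract makes all exa-cel patients treated in the enrolment period eligible, and section 9.2 has all of them invited. The wording is loose, but it does not show an intention to select.
- **The size is assumed and may be small.** Section 9.5 calls uptake unknown, and no mortality figure is given. One death fewer per 100 is well inside sampling error: the exact 95% interval for 5 of 100 is about 1.6% to 11.3%. This bears on severity. It does not remove a bias with a known direction for mortality.
- **The SAP may deal with it.** An unseen SAP could specify delayed entry. It cannot settle contradictory eligibility rules, and deaths never enrolled may not be recoverable later.

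**Conclusion.** The concern holds for mortality. Sections 9.1, 9.1.2 and 9.2 conflict on entry after transplant, and followed together they favour exa-cel. Early exa-cel mortality can be understated, absolutely and against allo-HSCT, to the extent that late entrants had to be alive to consent. For other outcomes the effect is indirect and its direction unknown.

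The size cannot be derived from the documents. Under the assumptions above, a true 1-year mortality of 5% would appear as about 4.8% to 4.1% at late-entry shares of 10% to 30%, with a spurious relative risk of roughly 0.95 to 0.82. The upper-bound case reaches 0.70. If few patients were infused before approval, the effect is negligible.

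This is a should-fix. The study is described in section 8.2 as hypothesis-generating and its focus is long-term, but the flaw lies in the entry rule for a primary comparison and is cheap to remove.

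**What to change.** 1. Reconcile sections 9.1, 9.1.2 and 9.2 with a single late-entry rule for exa-cel and allo-HSCT patients transplanted since exa-cel approval. The preferred rule is all consecutive patients at participating centres with valid registry consent, deaths included. State how patients who died with registry consent in place are handled.
2. Record the enrolment (consent) date for every patient.
3. For anyone whose inclusion depended on consent given after Day 0, start risk time at consent in the mortality and time-to-event analyses (delayed entry). Patients captured consecutively under existing registry consent do not need this.
4. Add a sensitivity analysis that excludes late entrants, including from the engraftment and Day-100 proportions. Keep them in the main versions of those proportions, because their early data are recorded.
5. Report the number of late entrants by cohort and name late entry among the limitations in section 9.9.

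The cost is protocol and SAP wording and one date field. A few patients contribute less early person-time.

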9.1.1 Study Population

All patients with TDT or SCD treated in participating centers reporting data to EBMT or CIBMTR and receiving exa-cel or allo-HSCT will be the source population for this long-term follow-up study.

To address the study objectives, the following longitudinal cohorts will be established within each registry:

- 1. Patients who received exa-cel for treatment of TDT (TDT Exa-cel Cohort)
- 2. Patients who received exa-cel for treatment of SCD (SCD Exa-cel Cohort)
- 3. Patients who received allo-HSCT for treatment of TDT (TDT Allo-HSCT Cohort)
- 4. Patients who received allo-HSCT for treatment of SCD (SCD Allo-HSCT Cohort)

9.1.2 Inclusion and Exclusion Criteria

This study will have broad inclusion and minimal exclusion criteria. To be eligible for inclusion, patients must be:

- receiving an HSCT from a study-participating transplant center reporting data to the respective transplant registry; and
- receiving exa-cel or allo-HSCT for treatment of TDT or SCD from the date of approval of exa-cel through the end of the enrollment period.

For the Allo-HSCT Cohorts, patients must be of an age that corresponds with the exa-cel label current at the time of transplant.

All patients must additionally provide informed consent / assent for registry / study data collection.

For the Allo-HSCT Cohorts, patients receiving transplants with any donor type and cell source used during routine standard of care will be eligible for study enrollment.

Patients treated with alternative gene therapies or experimental therapies will not be included. No additional exclusion criteria will be implemented.

The inclusion criteria may be further modified as appropriate, e.g., to allow transplant centers from European countries other than Germany, France, Italy, or UK to be included if exa-cel becomes available during the proposed study enrollment period in those countries.

